6.10 Ask Suicide-Screening Questions (asQ) Tool

The asQ Tool was created by the National Institute of Mental Health as a suicide risk screening tool for ages 8 years and above. Prior to initiating the asQ, the treating clinician will use their judgement to answer the following questions: does the participant (1) have the language skills

adequate to understand death and suicide and (2) the verbal ability to respond to “yes/no” and “how/when” questions about suicide.

- **If yes**, proceed to asQ. The participant should be excluded from the study if further clinical assessment and/or judgement are needed.
- **If no or < 8 years old**, do not screen for suicidal ideation.

The asQ tool uses 4 screening questions. If the participant answers “no” to all of the screening questions, they are not identified as a suicide risk and the screening is complete. If the participant answers “yes” to any of the questions, they are identified as a positive screen and are asked a 5th question to assess acuity of the suicidality. If the participant answers “yes” to the 5th question, they are identified as an acute positive screen, if they answer “no” they are identified as a non-acute positive screen.³⁵ All sites should follow local guidelines if a participant screens positive for suicidality. Per eligibility criteria, a participant who has an acute positive screen at Screening will be excluded from the study.

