	
4. For participants \geq 8 years old at the time of consent, participant has a history of suicidality or positive screen on Ask Suicide-Screening Questions (asQ) Tool.5. Participant is currently in or plans to participate in another interventional study.6. Participant has a known hypersensitivity to guanfacine.7. Participant has had a previous guanfacine treatment failure, as determined by their primary treating physician.8. Participant has had a change in another medication intended to treat symptoms of hyperactivity, inattention, and impulsivity within the last 2 weeks.9. Participant has had a seizure within the last 6 months.10. Participant has had a change in their anti-convulsant dose within the last 4 weeks.11. Participant has a cardiac-related condition including:
a. Significant symptomatic bradycardia;b. 2nd degree or 3rd degree (complete) heart block;c. Baseline heart rate (HR) or systolic blood pressure (BP) $>$ 2 standard deviations (SD) below mean for age as determined by medical examination;d. History of aborted sudden cardiac death, unexplained syncope or near syncope, or historical use of a pacemaker as determined by medical history will require clearance by cardiology prior to enrollment;e. Known history of congenital heart disease which requires ongoing care for monitoring or management will require clearance by cardiology prior to enrollment.12. Participant has a history of untreated severe obstructive sleep apnea defined as obstructive apnea hypopnea index (OAHI) \geq 10 events per hour or aortic regurgitation (AR). Participants with an OAHI index $>$ 10/hr are eligible if managed with continuous positive airway pressure (CPAP).13. Participant has untreated thyroid disease.14. Participant has a known hepatic impairment defined as aspartate aminotransferase (AST) or alanine aminotransferase (ALT) $>$ 2x the upper limit of normal (ULN) for age.15. Participant has known impending or renal failure defined as:
a. Anuria diagnosed within 12 hours prior to enrollment;b. Requiring renal replacement therapy.16. Participant is pregnant (refer to Section 7.6.1).17. Participant has any condition which would make the participant, in the opinion of the investigator, unsuitable for the study.
--	---

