6.2 Screening (Day -29 to 0)

The investigator will screen participants in accordance with the eligibility criteria detailed previously (Section 5.2). The investigator will not exercise selectivity so that bias is prevented.

The following assessments/procedures will occur during the Screening period:

- Informed consent/assent
- Demographics, including identified gender, race, ethnicity, and date of birth
- Complete Medical history
- Physical exam, including weight and height
- Vital signs, including BP and HR
- Concomitant medications of interest
- ECG
- Lab assessments for baseline complete blood count (CBC) w/differential, basic metabolic panel (BMP), liver function tests (LFTs), Thyroid function studies (Thyroid Stimulating Hormone [TSH], free T4)
- For participants who have reached menarche only, pregnancy test (urine or blood test is acceptable)
- CGI-S for Eligibility (Section 6.9.3)
- ABC for Eligibility (Section 0)
- asQ for Eligibility, as appropriate, for participants \geq 8 years old who do not have prior known suicidality (Section 6.10)
- AEs directly related to study procedures

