15.7 Protocol Deviations

A protocol deviation is any noncompliance/unplanned excursion from approved investigational plan (e.g., protocol, MOP), or ICH GCP guidelines. The noncompliance may be on the part of the participant, investigator, or site staff. Because of deviations, corrective actions are to be developed by the site and implemented promptly. For this study, participant/guardian refusal for blood collection or any missing Clinical Outcome Assessment (Section [6.9](#)), **except** ABC score at Week 8 and those that are required to confirm eligibility, will not be considered protocol deviations in order to facilitate retention of participants for later study assessments, but will be tracked and reported to the sponsor.

Each investigator must adhere to the investigational plan as detailed in the study protocol and/or associated study materials (e.g. MOPs, Forms Instructions, User Guides etc.). Each investigator will be responsible for the training of delegated staff and enrolling only those participants who have satisfied all protocol eligibility criteria.

It is the responsibility of the site to use continuous vigilance to identify and report deviations within 5 working days of identification of the protocol deviation or within 5 working days of the scheduled protocol-required activity. All deviations must be promptly reported to the sponsor, via the DCC's EDC system.

All deviations from the protocol must be reported in the study records/data system. Protocol deviations must be submitted to the local IRB/REB/IEC per their guidelines. The site investigator and study staff are responsible for knowing and adhering to their IRB/REB/IEC requirements.

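### Section 6.10 restates the asQ exclusion for acute positives only, whereas exclusion criterion 4 bars every positive screen

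*Combined protocol and SAP*

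**What the plan says.** Exclusion criterion 4 applies to participants aged 8 or over at consent. In both the synopsis and Section 5.2 it excludes a child when the "participant has a history of suicidality or positive screen on Ask Suicide-Screening Questions (asQ) Tool". Nothing in it refers to acuity.

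Section 6.10 describes the tool. After a yes to any of the four screening questions, "they are identified as a positive screen and are asked a 5th question to assess acuity of the suicidality". A yes to the fifth question makes the screen an acute positive. After a no, "they are identified as a non-acute positive screen". On what follows, Section 6.10 makes three statements:

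- In the bullet on proceeding to the asQ: "The participant should be excluded from the study if further clinical assessment and/or judgement are needed".
- On clinical handling: "All sites should follow local guidelines if a participant screens positive for suicidality".
- In its last sentence, on eligibility: "Per eligibility criteria, a participant who has an acute positive screen at Screening will be excluded from the study".

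Section 6.2 states that "The investigator will screen participants in accordance with the eligibility criteria detailed previously", citing Section 5.2. It also lists the asQ as an eligibility assessment and refers the screener to Section 6.10 for it. Section 15.7 makes each investigator responsible for "enrolling only those participants who have satisfied all protocol eligibility criteria", and Section 4.10 makes meeting all the criteria part of the definition of enrollment.

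**The concern.** The closing sentence of Section 6.10 presents itself as a report of the eligibility criteria, but it is narrower than the criterion it reports. It comes just after positives have been divided into acute and non-acute, and it attaches exclusion to the acute group alone. A reader could easily infer that a non-acute positive is a matter for local clinical management and does not bar entry. The preceding sentence, which sends positives to local guidelines, supports that inference. Section 6.10 is also where Section 6.2 sends the person doing the screen.

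What is at stake is a safety exclusion in a vulnerable pediatric population. A non-acute positive child could be randomized in breach of criterion 4, which would be an eligibility deviation. The protocol treats the same risk as relevant on treatment: Section 7.1.2 lists suicidality by the asQ among the safety events of special interest. No efficacy analysis depends on this point.

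**Working it through.** The point involves no sample size, power or error rate, so the check is a comparison of texts.

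**Step 1: what counts as positive.** By Section 6.10, any yes among the four questions is a positive screen. The fifth question grades a result that is already positive; it does not undo it. The possible results are negative, non-acute positive and acute positive.

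**Step 2: apply each rule to each result.**

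| asQ result at Screening | Criterion 4 (synopsis, Section 5.2) | Last sentence of Section 6.10 |
|---|---|---|
| Negative | Not excluded on the asQ | Not named |
| Non-acute positive | Excluded | Not named |
| Acute positive | Excluded | Excluded |

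Criterion 4 excludes 2 of the 3 results and the sentence names 1. They differ on 2 − 1 = 1 result, the non-acute positive.

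**Step 3: does other text in Section 6.10 close the gap?** The clause on further assessment or judgement sits in the bullet about going on to the asQ, before positive results are defined, and is not tied to any result. It may catch many non-acute positives, but only at a clinician's discretion, whereas criterion 4 is unconditional. The local-guidelines sentence concerns management and states no exclusion.

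**Step 4: do other criteria close it?** The history limb of criterion 4 helps only in part. Section 6.2 reserves the asQ for children without previously known suicidality, so that limb applies to a screened child only if the answers themselves reveal a history. Criterion 17 (any condition the investigator considers unsuitable) is again a matter of judgement.

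**Step 5: who could be affected.** Eligible ages are 6 to 12, which is 12 − 6 + 1 = 7 age-years. The asQ covers ages 8 to 12, which is 12 − 8 + 1 = 5 of those 7. Within that range it is given only to children the clinician judges able to understand the subject and answer the questions. The documents give neither the share of children judged able nor the rate of non-acute positives, so no expected count can be derived.

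**The case against.** The strongest reply is that the two texts can both be obeyed. An acute positive is indeed excluded under criterion 4, so the sentence in Section 6.10 is true as far as it goes. It does not confine exclusion to acute positives, and nothing in the section permits a non-acute positive child to enroll. Silence in a procedures section does not waive an exclusion. Sections 4.10, 6.2 and 15.7 make the Section 5.2 list binding, and the sentence itself points back to that list. For harm to follow, a site would have to overlook a criterion printed twice, rely on one summary sentence, and also decide that the further-assessment clause did not apply. The MOP and eligibility eCRF are not among the documents. If the eCRF repeats criterion 4 in full, sites would see the correct rule at enrollment.

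Most of this stands. The sentence is an incomplete restatement, not a contrary rule; Section 5.2 governs; and the route to harm is narrow. It is also fair that one result in three counts labels, not children, and that 5 of 7 age-years is not a share of enrollment. But none of this makes the two statements of the asQ rule agree. That Section 5.2 governs is the reason that acting on the narrower sentence would be a deviation. What the eCRF says is unknown in either direction.

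**Conclusion.** The concern holds. Section 6.10 misreports criterion 4 by omitting the non-acute positive, in the section to which screeners are sent for this assessment. The discrepancy covers one of the three asQ results. Its practical reach is probably small, given the age limit and the requirement that the child be able to answer, but that is an inference and not an estimate. A wrongly randomized child is a possibility, not an expectation.

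The conclusion rests on reading a positive screen in criterion 4 as Section 6.10 itself defines it, and on criterion 4 stating the intended rule. Sample size, power and the primary analysis are unaffected. This is a minor correction, worth making because it concerns a safety criterion.

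**What to change.** Delete the word *acute* from the last sentence of Section 6.10, so that any positive screen at Screening excludes the participant. This matches criterion 4, which is the stricter and governing rule and is stated twice. Use the same wording in the MOP and the eligibility eCRF. If the sponsor's clinicians intended to exclude acute positives only, criterion 4 should be amended in both the synopsis and Section 5.2, leaving Section 6.10 as it is.

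The edit is one word plus a check of two supporting documents. It changes no visit, sample size or analysis. Under Section 14.3 an amendment goes through the central IRB and then each site's IRB of record, with approximately 17 sites planned. It would therefore be sensible to include the edit in the next amendment and tell sites of the correct reading in the meantime.

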6.11 Specimen Preparation, Handling, Storage, and Shipping

Samples collected for the research will be labeled with a unique number via a study provided barcode label. Instructions for collection, labeling, preparation, handling, and storage of specimens will be detailed in the MOP.

6.12 Study Product Description

Guanfacine hydrochloride immediate release, brand name Tenex, is a centrally acting small molecule antihypertensive that comes in a tablet form for oral administration. Guanfacine hydrochloride is a white to off-white powder that is sparingly soluble in water and alcohol and slightly soluble in acetone. The tablets contain the following inactive ingredients: FD&C Red 40 aluminum lake (1 mg tablets only), lactose, microcrystalline cellulose, providone, and stearic acid.³² United States commercially available guanfacine tablets will be purchased and used as the source for the manufactured 0.5 mg dose guanfacine capsules with matching placebo by the University of Iowa Pharmaceuticals (UIP) to be used in this study. Guanfacine tablets will be milled and placed into capsules of 0.5 mg of active product.

The placebo will be a study drug-matched capsule filled with microcrystalline cellulose.

6.13 Dosage and Study Drug Information

6.13.1 Dose Timing

Dose escalation

Study product will be administered once daily (q.h.s.) during the first 5 (+ 2) days of study product administration and then twice daily thereafter. Twice daily doses may be administered in uneven BID dosing; for example, a total daily dose of 2.0 mg can be divided into 0.5 mg in the morning and 1.5 mg in the evening, at the discretion of the clinical provider. Dose escalation will occur based on the details in **Table 3** with the highest dose being dose level 6. Participants in both the GIR and placebo arms will be evaluated for potential dose escalation every 5 (+ 2) days via a Dose Escalation Assessment (via telephone during Weeks 1-3 and 5-7 or in-person at Week 4) described in Section **6.8**. Parent/legal guardian will be asked to measure HR and BP prior to each dose escalation assessment. If there is a safety concern during the weekly Dose Escalation Assessments (via telephone during Weeks 1-3 and 5-7 or in-person at Week 4) as stated in Section **6.8**, or for any other reason, the sites will be instructed on the following:

1. Hold at current dose/schedule for 5 (+ 2) days (or advance directly to step #3 or step #5 below, if deemed appropriate by the clinical provider)

2. Reassess at next dose-escalation assessment
3. If sedation is a significant concern, divide the total daily dose and give higher dose proportion at bedtime (q.h.s); example: 2 mg totally daily dose split as 0.5 mg in the morning and 1.5 mg q.h.s and
4. Reassess at next dose-escalation assessment
5. If safety concern remains, reduce total daily dose to the lower dose previously tolerated

Table 3. Dose Escalation Plan*

Dose Level	Total daily dose for weight \geq 25 kg (mg)
1	0.5
2	1.0
3	1.5
4	2.0
5	2.5
6	3.0

* Parent/legal guardian will be asked to measure HR and BP prior to each dose escalation assessment.

6.13.2 Dose Discontinuation /Taper

If a participant randomized to receive GIR withdraws from study early or chooses not to continue treatment with GIR via standard of care at the end of Week 8 unmasking, a drug taper plan will be employed for all participants whose final drug dose is > 1 mg/day. The dose taper will be a decrease in increments of 1 mg every 3 days. The taper will last a maximum of 6 days, but may be shorter if starting taper dose is less than 3 mg/day. Study Diary will be completed during the discontinuation/taper period.

Participants receiving < 1 mg at the final study drug administration will stop study drug treatment and will follow procedures for early withdrawal/termination (as applicable) or will proceed to Telephone Safety Follow-up (Section [6.5](#)).

6.13.3 Formulation, Packaging, and Labeling

The University of Iowa will manufacture 0.5 mg GIR capsules and matching placebo capsules adhering to Good Manufacturing Practice (GMP) and United States Pharmacopeia and National Formulary (USP/NF) from the purchase of United States-marketed GIR uncoated tablets.

The study product will be packaged (80 capsules per bottle) into High Density Polyethylene (HDPE) bottles, with a length of polyester coil and desiccant pack, and sealed with polypropylene (PP) child-resistant induction-sealed closures.

The University of Rochester Clinical Materials Services Unit (CMSU) will package and label kits containing 4 bottles (80 capsules per bottle). The kit box label will include an unique Kit identification (ID) number and a masked packaging code (PO#). The four bottles inside each kit will include labels with the Kit ID Number (matching the Kit ID Number on the kit box), a PO#, and a bottle number (1 through 4). Each randomized participant will be assigned one 4-bottle kit box.

The study product will be distributed by the site to the participant. The site will provide enough study product per participant for weeks 1-4 (1 bottle) on the day of randomization and for weeks 5-9 (3 bottles) at the Week 4 visit. See MOP for more details.

6.13.4 Product Storage and Stability

The study products should be stored at a controlled temperature between 20°C and 25°C in a tight, light-resistant container. Upon receipt and quality audit release of the manufactured GIR and matching placebo, CMSU will store the GIR in an ambient warehouse storage space (between 20°C and 25°C) prior to distributing to the clinical study sites. The study product will ship to sites in a qualified, controlled room-temperature shipper, and include a temperature-monitoring device while in transit. The site must acknowledge receipt of the kits in order for them to be available for dispensing. See MOP for more details.

6.14 Preparation and Administration of Study Product

Study product will be packaged and shipped from University of Rochester's CMSU to local sites who will be masked to the study-treatment assignment. Description on the masking procedures will be provided in the MOP. Local sites will distribute the appropriate respective study product on 1) the day of randomization (Day 1), and 2) the Week 4 in-person clinical assessment.

Participants will self-administer each oral dose. If the participant is unable to swallow the capsule whole, instructions to open the capsule and mix with food will be provided.

6.15 Modification of Study Product for a Participant

Dose reduction may occur according to the details in Section [6.13.1](#). See MOP for more details.

6.16 Accountability Procedures for the Study Product(s)

Refer to MOP for more details.

6.16.1 Replacement Kits

If a study product bottle or kit is broken or unusable, a replacement kit with a new unique Kit ID Number will be provided. Replacement kits may be requested via contact information provided in the MOP. Any missed or forgotten doses will be documented in the Study Diary, refer to the MOP for details.

6.16.2 Disposition of Study Products Upon Study Completion or Expiration

Following notification from the sponsor, upon completion of the study, or upon notice of the study products' expiration, the study product should be disposed of at the site, after the drug accountability logs have been reviewed by the monitors, pursuant to the ICH/GCP guidelines and the investigators' institutional policies.

6.17 Concomitant Medications of Interest/Treatments

Concomitant medications of interest include the following: central nervous system (CNS) depressants (example: benzodiazepines, barbiturates, opioids), anti convulsants (example: carbamazepine), CNS stimulants or non-stimulants to treat ADHD (e.g., methylphenidate, dextroamphetamine, amphetamines, clonidine, atomoxetine, bupropion) and antibiotics (e.g., ciprofloxacin, clarithromycin, erythromycin, fluconazole, itraconazole, voriconazole, rifampin).

7 ASSESSMENT OF SAFETY

7.1 Adverse Events

An **adverse event (AE)** is any untoward medical occurrence in humans, whether or not considered drug-related, which occurs during the conduct of a clinical trial. Any change in clinical status, ECGs, routine labs, x-rays, physical examinations, etc. that is considered clinically significant by the study investigator is considered an AE.

A **suspected adverse reaction (SAR)** is any AE for which there is a reasonable possibility that the drug caused the event. A reasonable possibility implies that there is evidence that the drug caused the event. An **adverse reaction** is any AE caused by the drug.

A **serious, unexpected, suspected adverse reaction (SUSAR)** is defined as a SAR that is both serious and unexpected for which a reasonable causal relationship with the drug use is suspected but not confirmed.

7.1.1 Unexpected Adverse Event

An Unexpected Adverse Event is defined as any AE, of which the nature, specificity or severity is not consistent with the applicable product information (e.g., package insert/approved label) or investigational plan.

7.1.2 Safety Events of Special Interest (ESIs)

A safety ESI is a select safety event that could be related to the study drug. Safety ESIs will be solicited for their occurrence (No or Yes) at weekly dose-escalation assessments, including in-person assessments (Week 4 and Week 8), and the final telephone safety assessment (5 + 2 days) after the final dose of study drug. The safety ESIs documented will be assessed by the investigator/delegate (defined as a clinician licensed to make a diagnosis) for intensity, causality, and association to provide uniform data collection of all events. Any reported ESIs should be managed, as needed, according to clinical judgement and local guidelines.

Safety ESIs include:

- Syncope/passing out
- Sedation
- Trouble falling asleep
- Trouble staying asleep
- Trouble waking up
- Drowsiness
- Decreased Energy/Fatigue
- Trouble concentrating
- Trouble breathing
- Constipation
- Diarrhea
- Nausea
- Vomiting
- Skin rash
- Itching
- Change in appetite
- Anxious/fearful

- Sadness/depressed mood
- Self-injurious behavior
- Clinically significant hypotension, defined as systolic BP percentile less than the 5th percentile.^{31,34} This corresponds to systolic BP percentiles for neurotypical children under the 8th percentile for males and under the 10th percentile for females.
- Clinically significant bradycardia, defined as HR > 2 SD below mean for age

The following safety ESIs will only be assessed at in-person visits (Week 4 and Week 8):

- Any clinically significant cardiac event (e.g., clinically significant changes on ECG)
- Suicidality via the asQ Tool (see Section [6.10](#))

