2.1.2 Pediatric Labeling of Guanfacine

Adult: Guanfacine immediate release (GIR) is FDA approved for the management of hypertension. It may be given alone or in combination with other antihypertensive agents, especially thiazide-type diuretics.

Pediatric: Included on the GIR label: Safety and effectiveness in children under 12 years of age have not been demonstrated. There is no specific information included regarding the use for ADHD/hyperactivity, inattention, or impulsivity. Adverse reactions noted with guanfacine hydrochloride are similar to those of other drugs of the central α 2-adrenoreceptor agonist class: dry mouth, sedation (somnolence), weakness (asthenia), dizziness, constipation, and impotence. While the reactions are common, most are mild and tend to disappear on continued dosing. Adverse events (AEs) reported in post marketing at an incidence greater than 1% included dry mouth, dizziness, somnolence, fatigue, headache, and nausea.³²

There have been spontaneous post-marketing reports of mania and aggressive behavioral changes in pediatric patients with ADHD receiving GIR tablets. The reported cases were from a single center. All patients had medical or family risk factors for bipolar disorder. All patients recovered upon discontinuation of guanfacine tablets. Hallucinations have been reported in pediatric patients receiving guanfacine tablets for treatment of ADHD.

Included in the label for GER: INTUNIV® is indicated for the treatment of ADHD as monotherapy and as adjunctive therapy to stimulant medications. INTUNIV® was studied for the treatment of ADHD in three controlled monotherapy clinical trials (up to 8 weeks in duration) and one controlled adjunctive trial with psychostimulants (8 weeks in duration) in children and adolescents ages 6-17 who met DSM-IV® criteria for ADHD. The effectiveness of INTUNIV® for longer-term use (more than 8 weeks) has not been systematically evaluated in controlled trials.

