2.4.2 Risks of Guanfacine Hydrochloride

Adverse reactions associated with guanfacine hydrochloride include:

- Dry mouth
- Sedation (somnolence)
- Weakness (asthenia)
- Dizziness
- Constipation
- Impotence
- Decreased HR
- Decreased BP

Most reactions are mild and typically disappear after continued dosing.

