7.5 Collection Period and Reporting Procedures

AE information will be gained from direct monitoring of the study participants as well as from clinician observation and self-reporting by the study participants or their guardians. The investigator/delegate (defined as a clinician licensed to make a diagnosis) must document their

assessment of severity and causality in the participant records in a timely manner and submit safety reports as required by their institutional review board (IRB)/research ethics board (REB)/institutional ethics committee (IEC).

AEs, safety ESIs, SAEs and SUSARs will be collected for all participants, following the first study product administration through 5 (+ 2) days after the last study product dose. AEs directly related to study procedures (e.g., blood collection) during the screening period will also be collected.

Safety ESIs will be captured on the Dose Assessment Form electronic case report forms (eCRFs) to provide uniform data collection and will not be reported separately as AEs. As these are expected pre-specified safety ESIs, they will not be reported in an expedited manner but will be reviewed by the MM and the BPCA Data Safety Monitoring Board (DSMB) convened by NICHD and reported to the FDA in the annual report.

Safety ESIs that are associated with any of the criteria that define the event as an SAE will be reported on the AE/SAE CRF set.

Deaths occurring during the study participation, irrespective of causality will be reported on the AE/SAE CRF set.

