14.2 Assent Process

This study includes minor participants who may be enrolled in the study only with the consent of their parent(s)/legal guardian(s). The minor participant should be informed about the study to the extent compatible with their neurodevelopmental abilities. Participants who are nonverbal or minimally verbal, have significant intellectual disability, are younger than seven to ten years old (depending on local standards), or have marked thought disorganization or positive psychotic symptoms are very unlikely to be considered developmentally able to provide assent. Sites should follow the minimal age requirements for assent, per their local standards. If the Site PI/designee, who is a clinician licensed to make a diagnosis, judges the participant to be developmentally able to understand the concepts of voluntary participation in research, the participant will be given a simplified, developmentally appropriate assent form to review, will be asked to share any questions they may have, and then will be asked to sign and personally date the assent form.

Assent does not substitute for the permission form signed by the participant's parent(s)/legal guardian(s). Sites should consult with their institution's policies regarding enrollment of participants who are unable to provide informed consent.

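### Dry mouth, dizziness and headache are named in the protocol but not on the solicited ESI list, so their absolute incidence may be under-ascertained relative to the listed events

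*Combined protocol and SAP*

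**What the plan says.** Three parts of the protocol bear on this.

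**What is expected of the drug.** Section 2.1.2 gives the class reactions noted with guanfacine as "dry mouth, sedation (somnolence), weakness (asthenia), dizziness, constipation, and impotence". It then says separately that post-marketing events above 1% "included dry mouth, dizziness, somnolence, fatigue, headache, and nausea". Section 2.4.2 carries an eight-item risk list, introduced by "Adverse reactions associated with guanfacine hydrochloride include", which includes dry mouth and dizziness but not headache.

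**What is asked.** Section 7.1.2 states the purpose of the solicited list: "A safety ESI is a select safety event that could be related to the study drug". On method it says: "Safety ESIs will be solicited for their occurrence (No or Yes) at weekly dose-escalation assessments". The same questions are put at Week 4, Week 8 and the final safety call. There are 21 listed items, and two more are assessed only in person. Section 7.5 places the ESIs on the Dose Assessment Form.

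**How everything else is found.** Under section 7.5, AE information comes from "direct monitoring of the study participants as well as from clinician observation and self-reporting by the study participants or their guardians". Section 6.8 has AEs as well as ESIs recorded at each dose-escalation assessment. Section 10.2.2 makes AE incidence a safety endpoint. Section 10.4.2 summarizes AEs and ESIs by arm, but plans model-based estimates, adjusted for baseline covariates and cumulative dose, for ESIs only.

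**The concern.** A solicited list meant for events that might be drug-related would be expected to cover the symptoms the protocol itself ties to the drug. This one prompts for about half of the post-marketing events above 1% and leaves the rest to unprompted reporting. It also asks about items absent from 2.4.2, such as itching, rash and diarrhea. No reason is given for the selection.

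An event that is asked about at every contact will usually be recorded more completely than one that must be volunteered or noticed. The three missing symptoms are largely subjective. Section 14.2 contemplates "Participants who are nonverbal or minimally verbal, have significant intellectual disability" among those unlikely to be able to assent, and section 6.10 has the clinician judge language ability before the suicide screen. A parent may therefore not learn of a mild headache or dizziness without looking for it.

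At stake is the secondary objective, to characterize the safety profile. Section 2.2 says there has been no randomized, masked, placebo-controlled study of an ADHD medication in children with Down syndrome, so these rates would be a first reference. Dose is flexible, yet the three symptoms would also have no planned estimate adjusted for cumulative dose.

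**Working it through.** The documents state no figure on this point, so there is none to reproduce. The check is a comparison of lists, followed by an illustration on assumed values.

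**Step 1. Compare the lists.**

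| Named event | In 2.1.2 | In 2.4.2 | Nearest solicited ESI in 7.1.2 |
|---|---|---|---|
| Dry mouth | reaction; post-marketing | yes | none |
| Dizziness | reaction; post-marketing | yes | none |
| Headache | post-marketing only | no | none |
| Sedation/somnolence | reaction; post-marketing | yes | sedation, drowsiness |
| Fatigue | post-marketing | no | decreased energy/fatigue |
| Weakness | reaction | yes | decreased energy/fatigue |
| Nausea | post-marketing | no | nausea |
| Constipation | reaction | yes | constipation |
| Impotence | reaction | yes | none |
| Decreased HR | no | yes | bradycardia |
| Decreased BP | no | yes | hypotension |

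Of the six post-marketing events, 3 of 6 are unsolicited. Of the eight items in 2.4.2, dry mouth, dizziness and impotence are unsolicited, which is 3 of 8. Impotence is not pursued here, since participants are aged 6 to 12 years.

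**Step 2. Trace the route into the data.** The three symptoms can be recorded at every dose-escalation contact (6.8) and from the sources in 7.5. No symptom prompt for them is specified. In 10.4.2 they appear in the AE tables by system organ class and preferred term, and not in the adjusted ESI models.

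**Step 3. Illustrate the size.** With 60 participants randomized 2:1, the GIR arm has 60 × 2/3 = 40. Let p be the true incidence and s the share captured. Neither is in the documents, so both are assumed over a range.

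- Expected recorded cases = 40 × p × s.
- Chance of recording none = (1 − p × s)^40.

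| Assumed p | s = 100% | s = 50% | s = 25% |
|---|---|---|---|
| 5% | 2.0 cases; none 12.9% | 1.0; 36.3% | 0.5; 60.5% |
| 10% | 4.0 cases; none 1.5% | 2.0; 12.9% | 1.0; 36.3% |
| 20% | 8.0 cases; none about 0% | 4.0; 1.5% | 2.0; 12.9% |

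**Step 4. Effect on the comparison of arms.** Suppose capture s is the same in both masked arms.

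- Risk ratio = (s × p1)/(s × p0) = p1/p0, which is unchanged.
- Risk difference = s × (p1 − p0), which shrinks in proportion. With assumed rates of 20% and 5%, the difference is 15 points at full capture and 0.5 × 15 = 7.5 points at half. The risk ratio is 4 in both cases (20/5 and 10/2.5).

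**The case against.** The strongest reply is that nothing is lost from collection. All AEs are collected from first dose (4.7), they are recorded at every dose contact, and AE incidence is an endpoint. The parent is likely the main informant for ESIs and AEs alike, so the gap is between prompted and unprompted questioning of the same adult. This stands. A reader might infer that the rates rest on children who often cannot report. The documents do not support that: guardians, clinician observation and direct monitoring are named sources, and 14.2 gives no proportion of nonverbal children.

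Second, 7.1.2 describes the ESIs as select events, so it does not promise to cover every labelled reaction. That is right, and there is no contradiction in the text. It does not explain why less closely linked items are prompted while dry mouth and dizziness are not.

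Third, the trial is small. The only documented frequency is above 1%. At 1% to 5%, 40 children give 40 × 0.01 = 0.4 to 40 × 0.05 = 2 cases, so even full capture would describe these events poorly. This limits the gain without removing it. Prompting a parent may also fail to recover symptoms that only the child feels, and the documents do not show how much sensitivity would be added.

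Fourth, a reader might infer that dose escalation is left unguarded against dizziness. It is not. Section 6.8 requires HR and BP before each assessment and lets any AE or ESI judged unsafe prevent escalation, and syncope, hypotension and bradycardia are solicited. Those items do not measure the incidence of milder dizziness, and dry mouth and headache have no counterpart.

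Finally, the Dose Assessment Form and the Manual of Procedures are not among the documents. They may already carry these prompts or an open AE question.

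**Conclusion.** The point holds as one of uneven ascertainment. Dry mouth, dizziness and headache get no prompt specified in the protocol and no place in the adjusted ESI analyses. Their absolute incidence and risk difference may be under-ascertained relative to the listed ESIs.

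How far cannot be derived from the documents. The figures in the working rest on assumed incidence and capture and show only the direction and plausible scale.

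Two stronger readings should be resisted. One is that the safety profile as a whole is understated: the possible under-count concerns three symptoms, and it is a risk, not a demonstrated result. The other is that the comparison of GIR with placebo is distorted: the same method applies in both masked arms, and with equal capture the expected risk ratio is unaffected. Headache is also the weaker case of the three, since 2.1.2 reports it only as a post-marketing event and 2.4.2 omits it.

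This is a low-cost improvement to a secondary objective. It does not affect the primary analysis.

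**What to change.** 1. In 7.1.2, add dizziness/unsteadiness, dry mouth and headache to the Yes/No list, in wording a caregiver can answer from observation. Put the same items on the Dose Assessment Form, asked at the same contacts as the other ESIs. If the form already prompts them, align 7.1.2 with it.
2. In 10.4.2, state that solicited and unsolicited event rates will be presented separately. As listed ESIs, the three symptoms would then also enter the model-based analyses already planned there.
3. If any participants are assessed before the change, identify which list applied to them so that the two methods are not pooled unmarked.

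The cost is three items on an existing form, slightly longer calls, and higher event counts in both arms, which should be read as better capture. No extra visit or procedure is needed, and no change to any dosing or escalation rule is proposed.
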